17.4. Subject Death

17.4.1. Death Data Collection

All subject deaths must be reported by the investigator to Medtronic on an AE form (AE with outcome of death) as soon as possible after the investigator first learns of the death. In case of death, there should be one SAE with the outcome of death reported.

In the event of a subject's death, it is recommended that the implanted system be explanted and returned to Medtronic for analysis whenever possible per local process. Local laws and procedures must be followed where applicable.

System Interrogation Data Recommendations:

- After the subject has died but prior to explant, it is strongly recommended that the system be interrogated and a full summary interrogation (Interrogate All) performed when possible, and saved in a digital format (Save-to-Media). Store one copy of the save-to-media at the site and send a copy to Medtronic.
- Make the device interrogation/save-to-media file before any programming to prevent overwriting information in the device's memory and/or distinguishing between events detected during versus before the explant procedure.
- Recommend obtaining the exact date and time of death as lower temperatures after death can cause ERI and other "event flags" to be stored in the device memory.

If the system is not interrogated, an explanation must be entered on the AE form. For ICD systems, the ventricular tachycardia (VT) and ventricular fibrillation (VF) detection capabilities must be disabled to avoid inadvertent shocks. If any system component is returned to Medtronic, internal return product reporting systems may be used to gather additional information about the returned device/component.

A copy of the death certificate, if available and allowed by state/local law, should be sent to the Medtronic Attain Stability Quad Clinical Study team. When a death occurs in a hospital, a copy of the death summary report and all relevant hospital records should be sent to the Medtronic Attain Stability Quad Clinical Study team, if available. If an autopsy is conducted, the autopsy report should also be sent to the Medtronic Attain Stability Quad Clinical Study team if available and allowed by state/local law. When the death occurs at a remote site, it is the investigative site's responsibility to attempt retrieval of information about the death. Additionally, device disposition information should be updated. In summary, the following data will be collected:

- Date of death
- Detailed description of death
- Cause of death
- Relatedness to system and/or procedure
- Device interrogation and Save-to-Media (if available)
- Device disposition information
- Death summary/hospital records (if available and allowed by state/local law)
- Autopsy report (if available and allowed by state/local law)
- Death certificate (if available and allowed by state/local law)

17.4.2. Death Classification and Reporting

Sufficient information will be required in order to properly classify the subject's death. The Investigator shall classify each subject death per the following definitions:

Cardiac Death: A death directly related to the electrical or mechanical dysfunction of the heart.

Sudden Cardiac Death (SCD): Natural death due to cardiac causes, indicated by abrupt loss of consciousness within one hour of the onset of acute symptoms; preexisting heart disease may have been known to be present, but the time and mode of death are unexpected. If time of onset cannot be determined, SCD will alternatively be defined as any unexpected cardiac death occurring out of the hospital or in the emergency room as dead on arrival.

Non-sudden Cardiac Death: All cardiac deaths that are not classified as sudden deaths, including all cardiac deaths of hospitalized subjects on inotropic support.

Non-cardiac Death: A death not classified as a cardiac death.

Unknown Classification: Unknown death classification is intended for use only when there is insufficient or inadequate information to classify the death.

Table 15: Subject Death Classification Responsibilities

What is classified?	Who classifies?	Classification Parameters
Death Classification	Investigator	Sudden Cardiac, Non-sudden Cardiac, Non-cardiac, Unknown

The Clinical Events Committee will review all deaths and provide a final adjudication of the death classification.

Regulatory reporting of Subject Deaths will be completed according to local regulatory requirements.

17.5. Product Complaint Reporting

Product complaint reporting and vigilance reporting are applicable and AEs related to any market-released device during the study must be reported. The reporting of product complaints is not part of the Attain Stability Quad Clinical Study and should be done in addition to the AE reporting requirements. Refer to local regulations for reporting requirements.

Product Complaint: Any written, electronic or oral communication that alleges deficiencies related to the identity, quality, durability, reliability, safety, effectiveness or performance of a medical device that has been placed on the market.

- Abuse: Abnormal use (definition acc. #4.1 of Meddev 2.12-1 rev8)
- Misuse: Use error (definition acc. #4.20 of Meddev 2.12-1 rev8)

It is the responsibility of the investigator to report all product complaint(s) associated with a medical device distributed by Medtronic, regardless whether they are related to intended use, misuse or abuse of the product. Reporting must be done immediately and via the regular channels for market-released products. The reporting of product complaints by the clinical team must be done according to the local Standard Operating Procedures. Medtronic will notify the regulatory authorities (e.g. Competent Authority) as applicable for the following incidents immediately upon learning of them:

- Any malfunction or deterioration in the characteristics and/or performance of a device, as well as any inadequacy in the labeling or instructions for use which led or might have led to the death or serious deterioration in the state of health of a patient, user, or other person.
- Any technical or medical reason resulting in withdrawal of a device from the market by the manufacturer.
- Any serious deterioration in the state of health, including:
 - Life-threatening illness or injury
 - Permanent impairment of a body function or permanent damage to a body structure
 - A condition necessitating medical or surgical intervention to prevent permanent impairment of a body function or permanent damage to a body structure

18. Data Review Committees

18.1. Clinical Events Committee

The study will utilize a Clinical Events Committee (CEC). At regular intervals, an independent CEC will review events and adjudicate at a minimum all system, and procedure-related events. Additionally, the CEC will provide an adjudication of the death classification for all reported deaths.

The CEC will consist of a minimum of three (3) non-Medtronic-employed physicians that are not participating investigators for the study, including a CEC chairperson.

Medtronic personnel may facilitate and participate in CEC meetings but will be non-voting members.

For AEs and deaths reviewed by the CEC, Medtronic will provide the CEC with the Investigator's description and classification and supportive documentation (when available). The CEC is responsible for reviewing the Investigator's assessment and supportive documentation (when available), reviewing applicable definitions, and determining final classifications for all adjudication parameters. For AEs, classification includes system/procedure relatedness and complication or observation. Additionally, the CEC will provide an adjudication for all reported deaths, including system/procedure relatedness and cardiac relatedness.

If the CEC disagrees with the investigator's classification of the event, the difference will be provided to the investigator. If the investigator agrees with the CEC's adjudication, the CRF documenting the AE will be updated accordingly.

If the investigator does not agree with the CEC's adjudication classification, both determinations will be provided within the final report; however the CEC's adjudication will be used for data analysis. The disagreement will also be included in reporting to ethics committees and regulatory authorities, if required.

18.2. Data Monitoring Committee

A Data Monitoring Committee (DMC) will not be utilized for this study considering:

- An independent CEC will be formed to adjudicate at minimum all system and procedure related events and all deaths.
- This study does not meet FDA's recommended criteria (Guidance for Clinical Trial Sponsors: Establishment and Operation of Clinical Trial Data Monitoring Committees) for when a study should use a DMC, primarily because the study is not evaluating the effectiveness of a treatment intended to prolong life or reduce the risk of a major adverse health outcome.
- As a result of risk analysis and mitigation efforts as outlined in Section 16, any residual risk associated with this study is considered low and acceptable.
- The Attain Stability Quad MRI SureScan LV Lead (Model 4798) is a modification of the currently market approved Attain Performa lead Models 4298, 4398, and 4598 is a modification of the currently market approved Model 4396 LV lead. The Attain Stability Quad lead Model 4798 has a similar electrode spacing as the Attain Performa lead Models 4298, 4398, and 4598.
- Study will be conducted under FDA oversight via an investigational device exemption (IDE).

19. Statistical Design and Methods

This section presents statistical considerations for the study design and provides a high-level description of planned analysis and reporting. More details will be given in a separate Statistical Analysis Plan (SAP) that will be completed before data freeze for the primary objective analysis. Any deviation to the pre-specified statistical analyses will be noted in the study report. The analysis of the study objectives will be completed when the sample size requirements (see Table 18) for all the study primary and secondary objectives are met. An interim analysis will be conducted when 360 subjects are enrolled in the study. This interim analysis is specifically designed for one of the secondary objectives (details in Section 19.2.2).

19.1. Primary Objectives

19.1.1. Primary Safety Objective

Objective

The Attain Stability Quad MRI SureScan LV Lead (Model 4798) will be considered safe if the probability of subjects free of Model 4798 lead-related complications at 6 months post-implant is greater than 87% (i.e., the lower bound of a one-sided 97.5% confidence interval must be greater than 87%).

Hypothesis:

$$H_0: S_{(6\text{-month})} \leq 87\%$$

$$H_1: S_{(6\text{-month})} > 87\%$$

where $S_{6\text{-month}}$ is the probability that a subject remains free from Model 4798 lead related complications through 6 months since implant.

Endpoint Justification

The study primary safety endpoint is Attain Stability Quad MRI SureScan LV Lead (Model 4798) related complications. All reported system and procedure-related AEs will be reviewed by an event review committee for LV lead relatedness and severity (see Section 18.1).

Utilizing lead related complication free survival probability to evaluate lead safety performance is widely accepted across cardiac device manufacturers and in the medical literature. Current already market-released Quadripolar LV lead 6-month safety performance is summarized in Table 16. The population performance of the Attain Stability Quad MRI SureScan LV Lead (Model 4798) is expected to be similar to the Medtronic Attain Performa Model 4298 lead.

Table 16: Safety Performance of Market Released Quadripolar Lead

	Medtronic Attain Performa	St. Jude Medical Quartet²²	Boston Scientific ACUITY X4²³
6-month LV Lead Complication Free Survival Probability Estimate	Model 4298 (Canted): 96.0% Model 4398 (Straight): 98.8% Model 4598 (S-shape): 96.2%	96% at 3 months	Straight: 96.5% Spiral: 98.5%

[figure not shown]
Statistical Analysis Methods

The primary objective will be analyzed using the time-to-first event Kaplan-Meier survival analysis method. Time 0 will be the day a subject undergoes the implant procedure of a Attain Stability Quad MRI SureScan LV Lead (Model 4798), which will be independent of success status of this implant procedure. Event date is the onset date of a subject's first complication that is related to the Attain Stability Quad MRI SureScan LV Lead (Model 4798) according to CEC adjudication. Subjects who undergo an Attain Stability Quad MRI SureScan LV Lead (Model 4798) implant attempt and do not experience any LV lead related complications will be censored at the time of their last known exposure to the Attain Stability Quad MRI SureScan LV Lead (Model 4798) for the survival analysis. For any lost-to-follow up subject, the last contact date will be used as the censor date. The 1-sided 97.5% confidence limit lower bound for the survival probability at 6 months (183 days) will be calculated using the log-log survival function approach (Kalbfleisch and Prentice 2002).

Sample Size Consideration

The primary safety objective performance criterion is set to be identical to Medtronic's Attain Performa Clinical Study (IDE Number: G120213). Therefore, the sample size calculation assumptions are derived based on the Model 4298 lead study results. The Attain Performa Model 4298 lead reported a 6-month complication free survival probably of 96.0%, with 97.5% Confidence Lower Limit of 94.3% (PMA-s clinical report).

The binomial calculation (Z-test) is used for initial sample size estimation. In order to preserve the overall study power, a type II error less than 10% was used for the sample size calculation. A sample size of 170 subjects completing their 6-month visit achieves greater than 90% power to detect a difference of 7% using the one-sided binomial test. The target significance level is 0.025. These results assume that the population proportion under the null hypothesis is 87% with an expected value of 94% (Figure 5). To account for 15% attrition, the enrollment size for this objective is 200.

Figure 5: Primary Safety Objective Sample Size Consideration by Difference Performance Assumption**Determination of Patients / Data for Analysis**

All consented subjects who undergo an Attain Stability Quad MRI SureScan LV Lead (Model 4798) implant attempt will be included in the analysis cohort. If a patient experiences multiple Attain Stability Quad MRI SureScan LV Lead (Model 4798) implant procedures during the study, the analysis cohort will only consider the first procedure. In the event multiple complications occur, the survival analysis endpoint is reached when the first Attain Stability Quad MRI SureScan LV Lead (Model 4798) related complication occurs.

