AE Assessment		✓	✓	✓	✓	✓	✓
Exit Subject							✓
Adverse Events (incl. AE with outcome of death)	As they occur						
Device Deficiencies							
System Modifications							
Study Deviations							

Table 9 below specifies permitted time windows for the required subject visits. Subject visit target dates and windows for each follow-up will be made available to the study site. Should a subject miss a visit or the visit falls outside the pre-specified window, a study deviation must be reported and the original follow-up schedule maintained for subsequent visits. Data analyses will include follow-up visits, regardless of whether the visit occurs within the window. Therefore, a late visit is preferred over a missed visit but must be accompanied by a deviation.

Table 9: Visit Windows

Visit	Window
Implant	0-30 days since Baseline Assessment
	(days since implant)
Pre-hospital discharge	0-7
3-month	76 - 106
6-month	183 - 213
12-month	350 - 380
18-month	518 - 578
24-month	701 - 761

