15.8.2.5. Pre-Hospital Discharge CRT System Testing and Programming

The following electrical testing will be performed using the implanted CRT-P or CRT-D device and the device programmer once the leads are connected to the CRT-P or CRT-D and pre-hospital discharge:

Lead Impedance

- Collect LV Lead Impedances using Vector Express on all vectors
- Perform a manual LV Lead Impedance Test for missing Vector Express values on vectors LV1 to RVcoil/Can, LV2 to RVcoil/Can, LV3 to RVcoil/Can, LV4 to RVcoil/Can and the final programmed vector
- Retain printouts at the site

Pacing Capture Thresholds (PCT)

- Perform PCTs at 0.5ms pulse width using Vector Express on all 16 vectors
- NOTE: A one time manual reprogramming the pulse width to 0.5ms will be required (Out of the box pulse width is set at 0.4ms)
- Perform a manual PCT test at 0.5ms pulse width for missing Vector Express values on vectors LV1 to RVcoil/Can, LV2 to RVcoil/Can, LV3 to RVcoil/Can, LV4 to RVcoil/Can and the final programmed vector
- Retain printouts at the site

Phrenic Nerve Stimulation (PNS)

- Test for presence of PNS at 8.0V at 0.5ms on final programmed vector
- NOTE: If PNS is present at 8.0V at 0.5ms, measure the PNS threshold at 0.5ms
- NOTE: PNS observed during this testing will not be considered an AE

Other Data Collection

Other data collected prior to hospital discharge following the implant includes;

- Rationale for selecting specific LV lead pacing vector for final programming
- Final device interrogation/save-to-media
- AE Assessment
- Study deviations
- Device deficiencies

15.9. 3 Months Post-Implant (remote or in office visit)

The 3 month scheduled follow-ups may be done remotely or inoffice. For remote visits, CareLink transmissions may substitute device interrogations. The following procedures will be completed and data will be collected at the 3 month Follow-up visit;

Lead Impedance

- Obtain LV Lead Impedance Test for the final programmed vector
- Retain printouts at the site

Pacing Capture Thresholds (PCT)

- Obtain PCTs at 0.5ms pulse width on the final programmed vector
- NOTE: A one time manual reprogramming the pulse width to 0.5ms will be required (Out of the box pulse width is set at 0.4ms)
- Retain printouts at the site

Phrenic Nerve Stimulation (PNS) (in office visit only)

- Test for presence of PNS at 8.0V at 0.5ms on final programmed vector
- NOTE: If PNS is present at 8.0V at 0.5ms, measure the PNS threshold at 0.5ms

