19.1.2. Primary Efficacy Objective #1**Objective**

The Attain Stability Quad MRI SureScan LV Lead (Model 4798) will meet the first primary efficacy objective if the proportion of subjects with at least one Attain Stability Quad MRI SureScan LV Lead (Model 4798) pacing vector having a pacing capture threshold (PCT) less than or equal to 2.5 V at 0.5ms pulse width at 6 months post-implant is greater than 80% (i.e., the lower bound of the one-sided 97.5% confidence interval must be greater than 80%).

Hypothesis

$H_0: P_{1_{6\text{-month}}} \leq 80\%$

$H_A: P_{1_{6\text{-month}}} > 80\%$,

[figure not shown]
where $P_{1_{6\text{-month}}}$ is the proportion of subjects with pacing voltage thresholds $\leq 2.5\text{V}$ at 0.5ms at 6 months follow-up visit post-implant for at least one LV lead pacing vector.

Endpoint Justification

The Attain Stability Quad MRI SureScan LV Lead (Model 4798) is equipped with the identical four electrodes to the Attain Performa LV leads. At the same time, the unique fixation mechanism may cause the distal end of the lead (tip) to be implanted away from the apical region of the heart, and therefore

the PCT may be slightly higher than the values observed in other Quadripolar LV leads. Therefore, we simulated the lead pacing threshold values based on the Attain Performa IDE study data, but excluding the PCT values collected at the most distal electrode. The simulation estimated that 89% of the subjects will achieve this endpoint (Figure 6).

Figure 6: Simulated PCT Distribution

Statistical Analysis Methods

All subjects with valid pacing thresholds measured at the 6 month follow-up visit will be included in this analysis. The proportion of subjects having at least one LV lead pacing vector with voltage thresholds less than or equal to 2.5V will be calculated. The lower bound of the 1-sided 97.5% Confidence Interval will be calculated using the Exact binomial method. Any subject in which no valid pacing threshold value is measured or who has an unable-to-capture result via all LV lead pacing vectors will be reviewed and adjudicated for a possible lead related AE but will not be included for this evaluation if the occurrence is deemed to be a system related event (e.g. lead dislodgement). However, this event may be counted against the safety primary endpoint based on the CEC's final classification.

Sample Size

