The primary efficacy endpoint will be analyzed using the Exact binomial method. In order to preserve the overall study power, a type II error less than 10% was used for the sample size calculation. A sample size of 145 subjects achieves 91% power to detect a difference of 0.1 using a one-sided binomial test at a target significance level of 0.025. These results assume that the population proportion under the null hypothesis is 80%, with an expected proportion of 90%.

Determination of Patients / Data for Analysis

All subjects enrolled into this study satisfying the following conditions will be included in this analysis:

- Successfully implanted with a Medtronic Quad CRT-P or CRT-D device and Attain Stability Quad MRI SureScan LV Lead (Model 4798)
- Completed 6-month follow-up visit
- Initially implanted Attain Stability Quad MRI SureScan LV Lead (Model 4798) is active at the 6-month follow-up visit
- At least one available and valid pacing threshold at the 6-month follow-up visit

19.1.3. Primary Efficacy Objective # 2

Objective

The Attain Stability Quad lead will meet the second primary efficacy objective if the proportion of subjects with at least one additional (or second) LV lead pacing vector having a pacing capture threshold less than or equal to 4.0 V at 0.5ms pulse width at 6 months post-implant is greater than 80% (i.e., the one-sided 97.5% lower confidence bound must be greater than 80%).

Hypothesis

$$H_0: P_{2_{6\text{-month}}} \leq 80\%$$

$$H_A: P_{2_{6\text{-month}}} > 80\%$$

where $P_{2_{6\text{-month}}}$ is the proportion of subjects with at least one additional LV lead pacing vector with pacing voltage thresholds $\leq 4.0V$ at 0.5ms at 6 months post-implant follow-up visit.

Endpoint Justification

The Attain Stability Quad MRI SureScan LV Lead (Model 4798) has 16 LV programmable pacing vectors . Subjects may have the pacing configuration programmed or reprogrammed at each clinic visit. A pacing threshold of 4.0 V will allow an adequate safety margin for programming LV pacing output. The maximum pacing amplitude of the CRT-P or CRT-D devices capable of programming pacing output to any LV lead pacing vector is 8.0V. In actual clinical practice, a less than 3V safety margin is used for the programmed LV lead pacing output in 99% of the patients.

Statistical Analysis Methods

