The efficacy endpoint #2 will be analyzed using the Exact binomial method. The proportion of subjects with at least 2 LV lead pacing vectors having voltage thresholds less than or equal to 4.0V at 0.5ms will be calculated. The lower bound of the 1-sided 97.5% Confidence Interval will be calculated using the Exact binomial method. Any subject in which no valid pacing threshold values are measured or with an Unable-to-capture result via all LV lead pacing vectors will be reviewed and adjudicated for possible lead related complications, and therefore may be counted against the study safety endpoint. However, it will be counted as a failure if there is not any additional LV lead pacing vectors (excluding the vector that is already include for the efficacy endpoint #1) are unable to capture with no lead related events reported.

Sample Size

The Attain Performa Model 4298 LV lead observed 97.7% subjects who were able to obtain a non-programmed pacing vector with PCT less than or equal to 4 volts. A sample size of 50 subjects completing the 6 month visit achieves 98% power to detect a difference of 0.18 using a one-sided binomial test at a target significance level of 0.025. These results assume that the population proportion under the null hypothesis is 80%, with the expected proportion of 97%.

Determination of Patients / Data for Analysis

All subjects enrolled into this study satisfying the following conditions will be included in this analysis:

- Successfully implanted with a Medtronic Quad CRT-P or CRT-D device and Attain Stability Quad MRI SureScan LV Lead (Model 4798)
- Completed 6-month follow-up visit
- Initially implanted Attain Stability Quad MRI SureScan LV Lead (Model 4798) lead is active at the 6-month follow-up visit
- At least one available and valid pacing threshold at the 6-month follow-up visit. In the event a subject failed to provide more than one valid pacing threshold value, that subject will be considered as not having at least one additional LV lead pacing with PCT \leq 4.0V at 0.5ms at 6 months post-implant follow-up visit

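### A silent, complete loss of capture first found at the 6-month visit and dated after day 183 counts against neither primary safety nor primary efficacy

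*Protocol*

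**What the plan says.** The rules below are the same in both protocol texts in the document.

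- **Safety (19.1.1).** The analysis is time to first complication related to the Model 4798 lead, as adjudicated by the Clinical Events Committee (CEC). "Event date is the onset date", and the decision rests on one landmark: "The 1-sided 97.5% confidence limit lower bound for the survival probability at 6 months (183 days").
- **Visit timing (15.4, Table 9).** The 6-month window is days 183 to 213 after implant. Out-of-window visits are kept: "Data analyses will include follow-up visits, regardless of whether the visit occurs within the window".
- **Testing before 6 months (15.9).** "The 3 month scheduled follow-ups may be done remotely or inoffice", and only the final programmed vector is tested then. After discharge, the 6-month visit is the first that requires an in-office test of all 16 vectors.
- **Efficacy #1 (19.1.2).** A subject with no valid threshold, or no capture on any vector, is reviewed and "will not be included for this evaluation if the occurrence is deemed to be a system related event (e.g. lead dislodgement"). The stated counterweight is that "this event may be counted against the safety primary endpoint". Cohort membership also requires this: "At least one available and valid pacing threshold at the 6-month follow-up visit".
- **Efficacy #2 (19.1.3).** The same cohort condition applies. Loss of capture is a failure only where the vectors "are unable to capture with no lead related events reported".
- **Sensitivity analysis (19.3.2).** Successfully implanted subjects outside the efficacy cohort are counted as failures.

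**The concern.** The efficacy exclusion is defensible only if the excluded subject is counted elsewhere. The protocol names safety as that place, but reads safety at the day on which the visit window opens. Whether a failure found at the visit is counted then turns on the onset date written for it, and the protocol states no rule for dating a failure that was silent until tested.

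The subjects at risk of being lost have complete loss of capture ruled system related, with lead dislodgement as the protocol's own example. An active-fixation lead is meant to prevent exactly this. Leaving such subjects out raises both the complication-free probability and the efficacy proportion, so the error runs towards meeting the objectives.

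**Working it through.** **The plan's own figure.** Section 19.1.1 states that 170 completers give more than 90% power (87% against 94%, one-sided 0.025) and that 200 must be enrolled. A Z-test using the variance of the observed proportion rejects at 156 or more event-free subjects of 170 and has 91.2% power; 170 / 0.85 = 200. The stated size is reproduced and is not at issue. The overall requirement in Table 18 is 400 at 6 months.

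**Tracing one subject.** Take a lead with no capture on any vector, first found on day 195, ruled system related and dated to that visit.

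| Analysis | Rule | Counted? |
|---|---|---|
| Primary safety | Onset by day 183 | No, 195 > 183 |
| Efficacy #1 | Excluded if system related | No |
| Efficacy #2 | Needs a valid threshold; failure only if no lead-related event is reported | No |
| Sensitivity, 19.3.2 | Outside cohort = failure | Yes, efficacy only |

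Only 1 of the 31 window days (day 183 itself) lies within the landmark.

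**Effect on safety.** Without censoring, with D events in n subjects, S = 1 − D/n and the log-log lower bound is S^exp(1.96·se), where se = √(D/[n(n−D)]) / |ln S|. The objective is met if the bound exceeds 87%.

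| n | Events D | S | Lower bound | Met? |
|---|---|---|---|---|
| 400 | 24 (expected at 6%) | 94.0% | 91.2% | yes |
| 400 | 24 + 4 = 28 | 93.0% | 90.0% | yes |
| 400 | 24 + 8 = 32 | 92.0% | 88.9% | yes |
| 400 | 24 + 12 = 36 | 91.0% | 87.7% | yes |
| 400 | 38 | 90.5% | 87.2% | yes (limit) |
| 400 | 24 + 15 = 39 | 90.25% | 86.9% | no |
| 170 | 10 | 94.1% | 89.3% | yes |
| 170 | 10 + 4 = 14 | 91.8% | 86.5% | no |

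The added counts are assumptions; the protocol gives none.

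**Effect near the null.** With n = 400 the chance of passing is P(D ≤ 38). It is 1.9% at a 13% event rate, 6.9% at 12% and 19.1% at 11%. If the true day-183 rate is 13% and 1 or 2 percentage points are dated too late, the false-pass probability rises from 1.9% to 6.9% or 19.1%. This applies only if those events truly began by day 183. The 1 to 2 points are assumed.

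**Effect on Efficacy #1.** Excluded subjects are added as failures and the exact lower bound is compared with 80%. With 130 successes in 145 it is 83.5%, falling to 80.8% with 4 added failures and 78.3% (not met) with 8. With 360 in 400 it is 86.6%, falling to 83.8% with 12, still met.

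**The case against.** Much can be said for the plan.

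- **Onset is not detection.** A dislodgement found on day 195 with onset placed at day 183 or earlier is a safety event under the stated rule. A reader might infer that every failure found at the 6-month visit escapes safety; the documents do not say so. What stands is that the outcome depends on an unstated dating convention. The analysis plan could supply one, but the efficacy exclusion and the landmark are already fixed in the protocol, and they do not meet for an event dated after day 183.
- **The window is sensible.** A visit on or after day 183 gives full follow-up to the landmark, and a true new onset on day 200 lies properly outside a 6-month probability. A reader might conclude that the landmark should move to day 213. That would change what is estimated by adding genuine later onsets, and would censor subjects last seen earlier in the window.
- **The group is narrow.** A lead with a measurable threshold above 2.5 V on every vector stays in as an Efficacy #1 failure. Loss of capture on the programmed vector by 3 months should show at that test, and adverse events are reported as they occur.
- **The sensitivity analysis counts these subjects.** This is true for efficacy, but it does not decide whether an objective is met and does nothing for safety. The opening of 19.3.2 could be read as placing all implanted subjects in the primary dataset, but the same section then treats those outside the cohort as a sensitivity case.
- **The 1 to 2 points are large.** Model 4298 had about 4% complications in total (100% − 96.0%), so they would be a quarter to a half of that lead's whole rate.

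**Conclusion.** The gap is real and narrow. It covers subjects with no valid threshold, or no capture on any vector, at the 6-month visit, ruled system related and dated to days 184 to 213. Under the stated rules they count against no primary objective, and the bias is towards passing.

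The size is unknown. At the planned 400 with performance near 94%, the safety limit of 38 events leaves room for 14 beyond the expected 24, so the conclusion is unlikely to change. It could matter with only the 170 or 145 subjects on which the individual objectives were sized, or if the true rate is close to the 87% criterion. The pass probabilities of 6.9% and 19.1% should not be read as the trial's error rate: they need an assumed share of misdated events, all with true onset by day 183. The bounds above assume no censoring.

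**What to change.** 1. **Section 19.1.1.** Count a CEC-adjudicated Model 4798-related complication first identified at the protocol 6-month visit as an event by day 183, unless onset after day 183 is documented.
2. **Sections 19.1.2 and 19.1.3.** Count as an efficacy failure in the primary analysis any subject excluded for system-related loss of capture or no valid threshold who is not a safety event by day 183.
3. Keep day 183 as the primary landmark. Report the estimate based on recorded onset dates as a sensitivity analysis and, optionally, a day-213 estimate.

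The change is wording and should be made before data freeze, so that the dating choice is not made after seeing the events. A few more events or failures may count, and event ascertainment will differ slightly from the earlier study that set the 87% criterion. Safety power is not a constraint: at 400 subjects and a true 94%, P(D ≤ 38) is 99.8%.
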